Genetic sample		X	Collect a pharmacogenomics sample only if the subject has a signed consent specific for this purpose. The pharmacogenomics sample can be collected anytime, but Day -1 is recommended. Informed consent for optional sub-studies (e.g., genetics research) must be obtained before collecting a sample.
Admission to clinical unit		X	
β -hCG = beta human chorionic gonadotropin, BP = blood pressure, FSH = follicle-stimulating hormone, HR = heart rate, KIM-1 = kidney injury molecule 1, NGAL = neutrophil gelatinase-associated lipocalin, SAE = serious adverse event.			

Table 4 Time and Events Table: Part 1 - Single Dose Escalation and Part 3 - Single Dose

Procedure	Day 1																	Day 2	Day 3	
	Hours relative to treatment administration																			
	Pre-dose	0	0.5	1	1.25	1.5	2	3	3.5	4	4.5	5	6	8	10	12	16	24	36	48
Randomization	X																			
12-lead ECG ¹	X		X	X		X	X	X		X			X			X		X		X
Vital signs (BP, HR, oral temperature, respiration rate)	X		X	X		X	X	X		X			X			X		X		X
Fasting clinical chemistry, hematology, and urinalysis ²																		X		
Treatment administration ³		X																		
Blood collection for pharmacokinetics ⁴	X		X	X	X	X	X	X	X	X	X	X	X	X	X	X	X	X	X	X
Urine collection for pharmacokinetics ⁵	X	X								X				X		X		X		X
Continuous cardiac monitoring ⁶	X	-----Continuous review----->																		
AE review		X	-----Continuous review----->																	
SAE review	X	-----Continuous review----->																		
Concomitant medication review	X	-----Continuous review----->																		
Discharge from inpatient unit ⁷																				X

AE = adverse event, BP = blood pressure, ECG = electrocardiogram, HR = heart rate, SAE = serious adverse event.

NOTES:

1. Triplicate 12-lead ECGs to be obtained at least 5 minutes apart within 1 hour before dosing. Single ECGs will be obtained at all other time points.
2. An aliquot of the urine sample will be collected for neutrophil gelatinase-associated lipocalin (NGAL) and kidney injury molecule 1 (KIM-1). These samples may be analyzed after the end of the study if a clinical signal is detected. Instructions for collection and storage of these urine samples are included in the Study Reference Manual. The albumin to creatinine ratio will be determined using the first morning void urine on Day 2.
3. GSK3342830 or placebo will be administered as a single IV infusion in the morning on Day 1. The planned infusion duration time is 1 hour.

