AE = adverse event, BP = blood pressure, ECG = electrocardiogram, HR = heart rate, SAE = serious adverse event.

NOTES:

1. Triplicate 12-lead ECGs will be obtained at least 5 minutes apart within 1 hour before the start of infusion (pre-dose) on Day 1. Single ECGs will be obtained at 0.5, 1, 1.5, 2, 3, 4, 6, and 12 hours after the start of infusion on Day 1 and Day 15, within 1 hour before the start of the morning infusion on Days 2, 3, 4, 5, 6, 7, 8, 9, 10, 11, 12, 13, and 14, and in the morning on Day 16.
2. Vital signs will be measured within 1 hour before the start of infusion (pre-dose) and at 0.5, 1, 1.5, 2, 3, 4, 6, and 12 hours after the start of infusion on Days 1 and 15, within 1 hour before the start of the morning infusion and on Days 2, 3, 4, 5, 6, 7, 8, 9, 10, 11, 12, 13, and 14, and in the morning on Day 16.
3. An aliquot of the urine sample will be collected for neutrophil gelatinase-associated lipocalin (NGAL) and kidney injury molecule 1 (KIM-1). These samples may be analyzed after the end of the study if a clinical signal is detected. Instructions for collection and storage of these urine samples are included in the Study Reference Manual. Hematology assessments on Days 5 and 15 will also include total iron, total iron binding capacity, ferritin, haptoglobin, ceruloplasmin and reticulocytes. The albumin to creatinine ratio will be determined using the first morning void urine on Days 5 and 15. Urinalysis assessments before dosing on Day 15 will also include urine color.
4. GSK3342830 or placebo will be administered as a single IV infusion in the morning on Day 1, TID IV infusions (approximately every 8 hours) on Days 2, 3, 4, 5, 6, 7, 8, 9, 10, 11, 12, 13, and 14, and as a single IV infusion in the morning on Day 15. The planned infusion duration time is 1 hour.

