7.3.4. Vital Signs

Vital signs should be taken with the subject in a semi-supine position, having rested in this position for at least 5 minutes and will include temperature, systolic and diastolic BP, pulse rate, and respiratory rate. Refer to Section [5.4.5](#) for vital sign stopping criteria.

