9.4. Key Elements of Analysis Plan

9.4.1. Primary Analyses

Safety Analyses

The following safety evaluations will be performed:

- Monitoring for AEs
- Routine clinical laboratory tests including chemistry, hematology, and urinalysis
- Vital signs
- Twelve-lead ECG readings
- Continuous cardiac monitoring (dual-lead telemetry)

Safety endpoints will include AEs, clinical laboratory test results (chemistry [including liver function parameters], hematology, and urinalysis), vital signs (BP, heart rate, respiratory rate, and body temperature), and 12-lead ECG readings.

All safety data will be presented in data listings. Subject demographics, medical history, and prior and concomitant medications will be summarized for each dose level using descriptive statistics. For continuous variables, these summaries will include number of subjects, mean, median, standard deviation, minimum, and maximum.

For categorical variables, the summaries will include frequencies and corresponding percentages. No inferential hypothesis testing will be performed on the safety variables.

Adverse events will be coded using the MedDRA classification system.

Treatment-emergent AEs will be defined as any AEs, regardless of relationship to study drug, that occur after the dose of study drug until the Follow-up visit. The treatment-emergent AEs will be summarized for each dose level at AE onset for the overall number of AEs and percentage of subjects who experience them. The total number of AEs will be summarized by dose level and overall. The AEs will be further summarized by severity and relationship to the study drug. If relationship information is missing, the AE will be considered treatment related. Listings for the subsets of SAEs

and treatment-related SAEs will be provided. The SAEs and number of AEs leading to discontinuation will be summarized. The incidence of AEs will also be summarized by system organ class and preferred term.

Clinical laboratory test results, vital signs, and 12-lead ECG results will be summarized by actual values and change from baseline. Clinical laboratory values that are outside of the reference ranges will be flagged and evaluated for clinical significance by the investigator. Any 12-lead ECG abnormalities will be summarized by each dose level. Physical examination findings and cardiac telemetry results will be listed.

Detailed descriptions of the analyses in this study will be presented in the RAP.

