## 1. REPORTING & ANALYSIS PLAN SYNOPSIS

Overview	Key Elements of the RAP
Purpose	
The purpose of this reporting and analysis plan (RAP) is to describe:
 
 
Any planned analyses and output to be included in the clinical study report for Protocol 204847.
 

Protocol	
 
This RAP is based on the original protocol (Dated: 18-FEB-2016) of study 204847 (GSK Document No. : 2015N257523_00).
 

Primary Objective	
 
For Part 1, to investigate the safety and tolerability of GSK3342830 after administration of single IV doses in healthy adult subjects
 
For Part 2, to investigate the safety and tolerability of GSK3342830 after administration of repeat IV doses in healthy adult subjects
 
For Part 3, to investigate the safety and tolerability of GSK3342830 after administration of a single IV dose in healthy adult Japanese subjects
 

Primary Endpoint	
 
Clinical safety data from adverse events (AEs), clinical laboratory tests, vital signs (blood pressure, heart rate, temperature, and respiration rate), and 12-lead electrocardiogram (ECG) readings
 

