<=30	xx (xx%)	xx (xx%)	xx (xx%)	xx (xx%)
>30-<=59	xx (xx%)	xx (xx%)	xx (xx%)	xx (xx%)
>=60	xx (xx%)	xx (xx%)	xx (xx%)	xx (xx%)
QTcF (msec)				
n	xx	xx	xx	xx
<=30	xx (xx%)	xx (xx%)	xx (xx%)	xx (xx%)
>30-<=59	xx (xx%)	xx (xx%)	xx (xx%)	xx (xx%)
>=60	xx (xx%)	xx (xx%)	xx (xx%)	xx (xx%)

*Note to Programmer: Continue for all treatments in Part 1, Part 2, and Part 3. Present Part 2 and Part 3 on separate pages.*

Note: Baseline is defined as the last nonmissing measurement before dosing for the respective treatment period.  
Unscheduled measurements are not included in this summary table except when calculating baseline.

GlaxoSmithKline  
 Example : VS1  
 Protocol : 204847  
 Population : Safety

Table 2.16  
 Summary of Vital Signs

Study Part: 1

Vital Sign	Group	N	Planned Relative Time	n	Mean	SD	Median	Min.	Max.
XXXXXXXX (XXX)	GSK3342830 250 mg	XXX	Baseline	xx	xx.x	xx.xx	xx	xx	xx
			Day 1 - 0.5 HR	xx	xx.x	xx.xx	xx	xx	xx
			...						
			Follow-Up	xx	xx.x	xx.xx	xx	xx	xx
XXXXXXXX (XXX)	GSK3342830 500 mg	XXX	Baseline	xx	xx.x	xx.xx	xx	xx	xx
			...						
XXXXXXXX (XXX)	...	XXX	Baseline	xx	xx.x	xx.xx	xx	xx	xx
			...						

*Note to Programmer: Continue for all treatments in Part 1, Part 2, and Part 3. Present Part 2 and Part 3 on separate pages. Timepoints for Part 1 and Part 3 are Baseline, Day 1 - 0.5 HR, Day 1 - 1 HR, Day 1 - 1.5 HR, Day 1 - 2 HR, Day 1 - 3 HR, Day 1 - 4 HR, Day 1 - 6 HR, Day 1 - 12 HR, Day 2, Day 3, Follow-Up. Timepoints for Part 2 are Baseline, Day 1 - 0.5 HR, Day 1 - 1 HR, Day 1 - 1.5 HR, Day 1 - 2 HR, Day 1 - 3 HR, Day 1 - 4 HR, Day 1 - 6 HR, Day 1 - 12 HR, Day 2 through Day 14, Day 15 - 0.5 HR, Day 15 - 1 HR, Day 15 - 1.5 HR, Day 15 - 2 HR, Day 15 - 3 HR, Day 15 - 4 HR, Day 15 - 6 HR, Day 15 - 12 HR, Day 16, and Follow-Up. Vital sign measurements summarized are: Systolic Blood Pressure (mmHg), Diastolic Blood Pressure (mmHg), Oral Temperature (C), and Pulse Rate (beats per min).*

Note: Baseline is defined as the last nonmissing measurement before dosing.  
 Unscheduled measurements are not included in this summary table except when calculating baseline.

GlaxoSmithKline  
Example : VS1  
Protocol : 204847  
Population : Safety

Page 1 of n

Table 2.17  
Summary of Change from Baseline in Vital Signs

Note to programmer: Please use the shell from Table 2.14 and include only Planned Relative Time after Baseline.

GlaxoSmithKline  
 Example : PK01  
 Protocol : 204847  
 Population : PK

Table 3.01  

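### The SAP's vital-signs table and listing shells leave out respiration rate, a named primary-endpoint variable, and the Part 2 Day 15 pre-dose reading

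*SAP*

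**What the plan says.** The SAP synopsis gives the primary endpoint as "Clinical safety data from adverse events (AEs), clinical laboratory tests, vital signs (blood pressure, heart rate, temperature, and respiration rate". SAP 2.2 repeats this for Parts 1, 2 and 3. Protocol 9.4.1 lists the same variables among the safety endpoints: "vital signs (BP, heart rate, respiratory rate, and body temperature), and 12-lead ECG readings". It adds that vital signs will be summarised both as measured and as change from baseline.

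Collection is not in doubt. Protocol 7.3.4 says the assessment "will include temperature, systolic and diastolic BP, pulse rate, and respiratory rate", and the schedule rows in protocol 7.1 read "Vital signs (BP, HR, oral temperature, respiration rate". For Part 2, note 2 to protocol Table 5 says "Vital signs will be measured within 1 hour before the start of infusion (pre-dose" and applies this to Days 1 and 15.

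SAP Table 3 plans a value summary, a change-from-baseline summary and a listing under one general vital-signs row. SAP 7.1.1 refers to Appendix 11 for the details. There:

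- The Table 2.16 note says "Vital sign measurements summarized are: Systolic Blood Pressure (mmHg), Diastolic Blood Pressure (mmHg), Oral Temperature (C), and Pulse Rate (beats per min".
- The Table 2.17 note says "Please use the shell from Table 2.14 and include only Planned Relative Time after Baseline".
- The Part 2 time points in Table 2.16 run "Day 2 through Day 14, Day 15 - 0.5 HR, Day 15 - 1 HR".
- The Listing 30 shell has columns for systolic and diastolic pressure, pulse and temperature. Listing 31 reuses it.

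SAP 2.1, on changes to the protocol's analysis, is marked not applicable.

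**The concern.** The general plan includes respiration rate, and the instructions a programmer would follow exclude it. The Table 2.16 list is worded as complete, so nothing invites a fifth parameter. If the shells are followed, the final study report shows no respiration-rate values by dose and time, and no change from baseline, for a variable that both documents place in the primary endpoint.

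Protocol 2.2 names possible effects on the respiratory cycle as an area for safety monitoring. The risk table in protocol 4.6.1 answers a rat tidal-volume finding with frequent vital-sign capture, although it calls that finding minimal and not statistically significant. Respiration rate is the only scheduled vital sign that measures breathing directly. An abnormal value that the investigator judges clinically significant would still be reported as an adverse event under protocol 12.5.1. A smaller shift with dose would appear in no display.

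**Working it through.** There is no plan figure to reproduce. The check compares what is collected with what is displayed.

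**Step 1: five measurements against each display.**

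| SAP item | Systolic BP | Diastolic BP | Temperature | Pulse / heart rate | Respiration rate |
|---|---|---|---|---|---|
| Table 2.16 | yes | yes | yes | yes | no |
| Table 2.17, read with the Table 2.16 shell | yes | yes | yes | yes | no |
| Table 2.17, read with the Table 2.14 shell as written | no | no | no | no | no |
| Listing 30 | yes | yes | yes | yes | no |
| Listing 31 (Listing 30 shell) | yes | yes | yes | yes | no |
| Clinical-importance ranges, 10.6.2 | yes | yes | no | yes | no |

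Table 2.14 counts subjects by QTc category and cannot hold vital signs. The display index and the Table 2.17 shell header both give shell VS1, the same as Table 2.16, so the intended reference is almost certainly Table 2.16. On either reading respiration rate is absent. The only safety figures are cytokine plots. So 4 of the 5 measurements are named in Table 2.16 and Listing 30, and 0 of the 4 vital-signs displays (Tables 2.16 and 2.17, Listings 30 and 31) show respiration rate.

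**Step 2: Day 15 in Part 2.** Protocol Table 5, note 2, schedules vital signs before the infusion on Day 15. The Table 2.16 time points go from Day 14 to 0.5 hours on Day 15. They match the time points of ECG Table 2.12, and protocol Table 5, note 1, schedules no Day 15 pre-dose ECG. A list carried over from the ECG table would explain the gap.

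**Step 3: number of readings.** Assume planned enrolment (48, 30 and 10) and no missed visits.

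- Times per subject after the first dose, Parts 1 and 3: 0.5, 1, 1.5, 2, 3, 4, 6, 12, 24 and 48 h = 10, plus follow-up = 11.
- Part 2: Day 1 (8) + Days 2 to 14 (13) + Day 15 pre-dose (1) + Day 15 after the start of infusion (8) + Day 16 (1) + follow-up (1) = 32.
- Total: 48 × 11 + 30 × 32 + 10 × 11 = 528 + 960 + 110 = 1,598.
- On active: 36 × 11 + 24 × 32 + 8 × 11 = 396 + 768 + 88 = 1,252.
- On placebo: 12 × 11 + 6 × 32 + 2 × 11 = 132 + 192 + 22 = 346.
- Day 15 pre-dose: 30 × 1 = 30. The other 1,598 − 30 = 1,568 fall at time points already in Table 2.16, so adding the parameter alone would display them.

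**The case against.** The strongest reply is that this is a drafting slip and not an analysis decision. The SAP names respiration rate wherever it defines vital signs, and neither SAP Table 3 nor the display index excludes any parameter. Only the detailed notes and shells drop it. That is a fair account of how the gap arose, but SAP 7.1.1 sends the reader to those shells for the details, so they need correcting.

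Three stronger readings are tempting, and the documents support none of them.

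- **That the data are lost.** They are collected, and SAP 10.3.3 calls for analysis datasets to CDISC standards. A missing descriptive display could be added later without bias, since safety is not formally tested.
- **That escalation decisions are affected.** All four displays are final-analysis deliverables in SAP Appendix 11. Escalation rests on a separate review of all preliminary safety data (protocol 9.3.2, SAP 3.1). No vital-sign stopping criterion in protocol 5.4.5 uses respiration rate.
- **That vital signs need a new listing of every subject.** The SAP limits laboratory and ECG listings to flagged values or subjects in the same way. Whether limited listings meet the protocol 9.4.1 commitment to list all safety data is a separate question, and it applies equally to those data.

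The count of readings shows how much goes undisplayed. It does not measure bias or a changed conclusion. Enrolment is approximate, and cohorts may be added or removed.

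**Conclusion.** The point holds as a reporting defect. One of five collected vital-sign measurements, named in the primary endpoint for every Part, is in none of the four planned vital-signs displays. This is contrary to the summaries promised in protocol 9.4.1, and SAP 2.1 declares no departure. In Part 2 the scheduled Day 15 pre-dose reading is also missing from Table 2.16 for all vital signs, one time point per subject. The conclusion assumes that the shells are programmed as written. It concerns the content of the final report only. It should be corrected before the final tables are programmed.

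**What to change.** 1. In the Table 2.16 note, add Respiration Rate (breaths per min) to the parameters and Day 15 pre-dose to the Part 2 time points.
2. In the Table 2.17 note, change the reference from Table 2.14 to Table 2.16.
3. Add a respiration-rate column to the Listing 30/31 shell. The ranges in SAP 10.6.2 cover only blood pressure and heart rate, so this column shows respiration rate only for values or subjects flagged on those. Tables 2.16 and 2.17 do the main work.
4. If respiration rate was left out on purpose, record that in SAP 2.1 as a change from protocol 9.4.1, with the reason.

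The cost is one parameter, one time point, one corrected reference and one column in existing shells. No new data collection is needed.

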4.3. Type and Number of Subjects

For Part 1, approximately 48 healthy adult subjects will be enrolled with approximately 8 subjects in each of the 6 planned cohorts. In each Part 1 cohort, approximately 6 subjects will be assigned to active treatment and approximately 2 subjects will be assigned to placebo. For Part 2, approximately 30 healthy adult subjects will be enrolled with approximately 10 subjects in each of the 3 planned cohorts. For Part 3, approximately 10 healthy adult Japanese subjects will be enrolled. In each Part 2 cohort and the Part 3 cohort, approximately 8 subjects will be randomized to receive active treatment and approximately 2 subjects will be randomized to receive placebo.

Additional subjects/cohorts may be enrolled to allow for evaluation of additional dose levels.

Decisions regarding replacement of subjects prematurely discontinued from study drug in any cohort will be made by the investigator and the GSK medical monitor on a case-by-case basis. Subjects may only be randomized to one cohort and may only participate in one part of the study.

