## 2.4. Statistical Hypotheses

No inferential hypothesis testing will be performed.

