
 
For the repeat dose cohorts (Part 2), the accumulation ratio (<math>R_0</math>) will be calculated as the ratio of <math>AUC(0-\tau)</math> on Day 15 to <math>AUC(0-\tau)</math> on Day 1 for each subject. The dosing interval (<math>\tau</math>) will be equal to 8 hours. Following log-transformation, <math>AUC(0-\tau)</math> of GSK3342830 on Days 1 and 15 will be analyzed by a mixed effect model, fitting dose, day, and dose-by-day interaction as fixed effects and subject as a random effect. For each dose, point estimate and 90% CI for the difference "<math>AUC(0-\tau)</math> on Day 15 - <math>AUC(0-\tau)</math> on Day 1" will be constructed using the appropriate error term. The point estimate and associated 90% CI will then be exponentially back-transformed to provide point and 90% CI estimates for the ratios "<math>AUC(0-\tau)</math> on Day 15: <math>AUC(0-\tau)</math> on Day 1." If dose-by-day interaction is not significant, then a single point estimate and 90% CI pooled across all doses for the ratio <math>AUC(0-\tau)</math> on Day 15: <math>AUC(0-\tau)</math> on Day 1 may be constructed with all estimates for each dose.
 

Model Checking & Diagnostics

 
Refer to Appendix 9: Model Checking and Diagnostics for Statistical Analyses.
 

Model Results Presentation

 
The point estimate and 90% CI for the accumulation ratios of <math>AUC(0-\tau)</math> on Day 15 to <math>AUC(0-\tau)</math> on Day 1 will be calculated.
 

Assessment

 
Steady state assessment of GSK3342830.
 

Endpoint(s)

 
An estimate of the slope (with corresponding 90% CI).
 

Model Specification

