Summary of Statistical Analysis of GSK3342830 Plasma Time Invariance in Part 2

Dose: XX mg

Parameter (Unit)	Day	N	Geometric LS Means	Regimen Comparison	Ratio of Geometric LS Means (%)	90% Confidence Interval of Ratio (%)	CVw(%)
AUC(0-inf) (Unit)	1	xx	x.xxx	15/1	x.xxx	(x.xxx, x.xxx)	x.xxx
AUC(0-tau) (Unit)	15	xx	x.xxx				

*Notes to programmer: Repeat for each dose level.*

Note: A linear mixed-effect model with group (group=1 for AUC(0-inf) on Day 1, and group=2 for AUC(0-tau) on Day 15) as a fixed effect and subject as a random effect was fitted to the natural log transformed PK parameters.

Source Data: Listing 46.

GlaxoSmithKline

Example : PK\_T1  
Protocol : 204847  
Population : PK Parameter

Page 1 of n

Table 3.12  
Summary of Statistical Analysis of GSK3342830 Plasma Accumulation Ratio in Part 2

Parameter (Unit)	Dose* (mg)	Day	N	Geometric LS Means	Regimen Comparison	Ratio of Geometric LS Means (%)	90% Confidence Interval of Ratio (%)	CVw(%)
AUC(0-tau) (Unit)	xx	1	xx	x.xxx	15/1	x.xxx	(x.xxx, x.xxx)	x.xxx
		15	xx	x.xxx				
	yy	1	xx	x.xxx	15/1	x.xxx	(x.xxx, x.xxx)	
		15	xx	x.xxx				
	zz	1	xx	x.xxx	15/1	x.xxx	(x.xxx, x.xxx)	
		15	xx	x.xxx				

Note: A linear mixed-effect model with dose, day, and dose-by-day interaction as fixed effects and subject as a random effect was fitted to the natural log transformed PK parameters.

\* If dose-by-day interaction is significant (p-value less than 0.05), then point estimate and 90% CI will be reported for each dose level.

Source Data: Listing 46.

GlaxoSmithKline

Example : PK\_T1  
Protocol : 204847  
Population : PK Parameter

Page 1 of n

Table 3.13  
Summary of Statistical Analysis of GSK3342830 Plasma Steady State Assessment in Part 2

Parameter	Days Included	Estimated Slope for Day	90% CI Lower-Upper
Ctrough (units)	3, 6, 9, 12, 13, 15	x.xxx	x.xxxx-x.xxxx

Note to programmer: If the 90% CI does not include zero, repeat the analysis without the data for the earliest day used in the previous analysis. Display the results for all models run.

Note: A mixed effect model will be fitted by dose and day (as a continuous covariate) as a fixed effect term and subject as a random effect term. No formal statistical hypothesis tested. Steady state is estimated to be achieved by the earliest day included in the analysis when the 90% CI of the slope includes 0.

Source Data: Table 3.06.

GlaxoSmithKline

Example : PK\_T2  
Protocol : 204847  
Population : PK Parameter

Page 1 of n

Table 3.14  

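### The Table 3.12 shell footnote makes the per-dose accumulation ratio and 90% CI conditional on an interaction p<0.05, against the unconditional rule in Protocol 9.4.2 and SAP 8.1.3.2

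*SAP*

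**What the plan says.** SAP 8.1.3.2 (accumulation ratio) fits a mixed model to log AUC(0-τ) on Days 1 and 15, with dose, day and dose-by-day interaction as fixed effects and subject as a random effect. Three rules then bear on what is reported.

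- **Per dose, no condition.** "For each dose, point estimate and 90% CI for the difference" between Day 15 and Day 1 will be constructed and back-transformed to a ratio.
- **Pooled, optional.** "If dose-by-day interaction is not significant, then a single point estimate and 90% CI pooled across all doses for the ratio" of Day 15 to Day 1 "may be constructed with all estimates for each dose". No significance level is given here.
- **Per dose, conditional.** The footnote on the dose column of shell Table 3.12 reads: "If dose-by-day interaction is significant (p-value less than 0.05), then point estimate and 90% CI will be reported for each dose level". This is the only place where 0.05 appears for this analysis.

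The SAP synopsis and Protocol 9.4.2 repeat the first two rules. SAP 2.4 also states: "No inferential hypothesis testing will be performed". Protocol 9.1 names accumulation among the items handled by estimation.

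**The concern.** Read by itself, the footnote lets an interaction test decide whether the model-based per-dose ratios are shown. Programmers work from the shell, so it could override the text. The test has 2 and about 21 degrees of freedom, and the sample size rests on feasibility (Protocol 9.2.1). A non-significant result would therefore be weak evidence that accumulation is the same at all doses.

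If the pooled ratio is then the only formal estimate, a higher ratio at the top dose is averaged with the lower doses, and the interval around that average is narrower than a single-dose interval. The top dose is where a reader would most want a separate estimate. Protocol Table 9 predicts a median AUC(0-24) of 3078 h•µg/mL at 4000 mg TID, against a NOAEL exposure of 2875. Its note says that the repeat-dose values were not simulated but were based on the single-dose simulation.

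**Working it through.** The plan states no power or precision for this test, so there is no figure to reproduce.

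**Inputs from the documents.** Protocol 4.3 gives "approximately 10 subjects in each of the 3 planned cohorts" for Part 2 and about 8 active subjects per cohort. That is 24 active subjects, with 2 interaction df and 24 − 3 = 21 error df. The test level is 0.05 (Table 3.12 footnote) and the intervals are 90%.

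**Assumptions.** The documents give no within-subject SD for AUC(0-τ), so the log SD σ runs from 0.05 to 0.30. True ratios are 1.05, 1.05 and 1.22. The rule examined is: per-dose intervals if p<0.05, otherwise the pooled interval alone.

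**Power.** Each subject's log Day 15 minus log Day 1 difference has variance 2σ². The noncentrality is λ = n·Σ(μᵢ − μ̄)²/(2σ²).

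- ln 1.05 = 0.0488 and ln 1.22 = 0.1989, a difference of 0.1501.
- Σ(μᵢ − μ̄)² = (2/3) × 0.1501² = 0.0150.
- At σ = 0.15, λ = 8 × 0.0150/(2 × 0.0225) = 2.67, and F(2,21) at 0.05 has 26% power.

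**Interval width.** With t(0.95; 21) = 1.721, the log half-width is 1.721·√2·σ/√8 for one dose and 1.721·√2·σ/√24 pooled. The ratio of the two is 1/√3 = 0.58. At σ = 0.15 the half-widths are 0.129 and 0.0745.

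- The pooled estimate centres on exp[(2 × 0.0488 + 0.1989)/3] = 1.10. A typical pooled interval is exp(0.0988 ± 0.0745) = 1.02 to 1.19, which excludes 1.22.
- A typical top-dose interval is exp(0.1989 ± 0.129) = 1.07 to 1.39.

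**Coverage of the top-dose ratio, by simulation (400,000 trials per row):**

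| Log SD | Power | Pooled CI covers, when pooled | Rule overall | Per-dose CI always |
|---|---|---|---|---|
| 0.05 | 99% | 0% | 89% | 90% |
| 0.10 | 52% | 5% | 49% | 90% |
| 0.15 | 26% | 29% | 42% | 90% |
| 0.20 | 16% | 50% | 54% | 90% |
| 0.30 | 10% | 70% | 70% | 90% |

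**Sensitivity.**

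- Ratios 1, 1 and 1.25: overall coverage is 80%, 49%, 41% and 53% at within-subject CVs of 10%, 15%, 20% and 30%, with power of 87%, 52%, 32% and 16%.
- Ratios 1, 1 and 1.5: power is 97% at CV 15% and 80% at CV 20%, with coverage of 88% and 74%.
- Equal ratios at all doses: coverage is 88%.

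**What linear kinetics predict.** Protocol 4.5 gives CL 0.93 mL/min/kg and V 0.121 L/kg. Then k = 0.93 × 60/1000/0.121 = 0.461 per hour, the one-compartment half-life is about 1.5 h, and the ratio at τ = 8 h is 1/(1 − exp(−8 × 0.461)) ≈ 1.03.

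**The case against.** Several stronger readings are tempting, and the documents do not support them.

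- **The plan requires pooling when the test is not significant.** No passage says so. The text only permits pooling. The footnote does not mention it, and the shell has three dose rows and no pooled row. The coverage figures describe one way of combining the footnote with the optional text.
- **Top-dose accumulation would be hidden.** It would not. Table 3.06 summarises the ratio by dose level, Listing 46 gives it per subject, and Table 3.07 gives geometric mean AUC(0-τ) by dose for Days 1 and 15. None depends on the test. Table 3.06 is an arithmetic summary with a 95% CI, however, and does not replace the model-based ratio and 90% CI.
- **Exposure limits or escalation are affected.** They are not. Limits are checked through AUC[0-8]×3 and Cmax in the dose-escalation displays. SAP Appendix 11 lists Table 3.12 as a final-analysis deliverable.
- **The test has low power whatever the data.** Power depends on an SD that the documents do not give. At a log SD of 0.05 the condition is nearly harmless. A ratio near 1.03 is predicted, so an excess at the top dose alone would need dose-dependent kinetics.

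The statement in SAP 2.4 adds little, since the protocol itself provides for the interaction check. It is also fair to say that a pooled interval does not claim to cover the top dose. What stands is the conflict over whether per-dose model-based results are always reported.

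**Conclusion.** The conflict is real and can be read straight from the documents: per-dose estimates are unconditional in the protocol and SAP text, and conditional in the shell. The statistical cost arises only if the footnote is followed and the pooled ratio is reported in place of the per-dose ratios. In that case, with ratios of 1.05, 1.05 and 1.22, top-dose coverage falls to about 42% to 54% at log SDs of 0.10 to 0.20, and is 89% at 0.05 and 70% at 0.30. In none of the settings examined does the condition improve on the 90% of the per-dose interval. The SDs and ratios are assumptions, so these figures show what the rule can do and are not a forecast for this trial. The consequence is confined to the final formal accumulation analysis, a secondary endpoint. The change is still worth making, because it restores what the protocol specifies.

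**What to change.** Delete the p<0.05 footnote from shell Table 3.12. Always report the geometric ratio and 90% CI for each dose; the rows already exist. If a pooled ratio is wanted, add it as a separate row labelled as pooled across doses, never as a replacement. Change the pooling sentence in SAP 8.1.3.2 and the synopsis to say that the pooled ratio is shown in addition to the per-dose ratios. The cost is one shell footnote and one sentence of SAP text (with its repeat in the synopsis); no new data or model is needed.
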